7.3 Pharmacokinetic and ATA Assessments

Blood samples for PK and ATA will be collected throughout the study per the sample collection schedule provided in [Table 3](#). Validated or qualified assays will be used to measure the concentrations of enfortumab vedotin ADC, TAB, and MMAE in serum or plasma. PK samples will be collected and archived for possible analysis of other enfortumab vedotin-related species, such as circulating metabolites of MMAE. A qualified assay will be used to determine the levels of ATA in serum.

Refer to the Central Laboratory Manual for information on collection, processing, storage, and shipment of sample.

7.4 Biomarker Studies

Samples for exploratory biomarkers will be collected at protocol-specified timepoints (see [Table 3](#) and [Appendix A](#)). Biomarker assessments will not be used for patient selection.

Methods of analysis may include IHC, next generation sequencing, PCR, mutation and gene expression profiling; T-cell receptor beta chain sequencing, flow cytometry and immunoassays.

7.4.1 Biomarkers in Blood

The primary effects of enfortumab vedotin on urothelial carcinoma tumor cells may lead to changes in the activation state of local, tumor-associated and peripheral immune cells. Biomarker assessments in blood samples may include but may not be limited to: markers of immune function, including abundance and phenotype of immune cell subsets, circulating

tumor DNA (ctDNA), and abundance of cytokines. These may provide insight into treatment-related changes in activation state of peripheral immune system associated with enfortumab vedotin-induced tumor cell death.

Table 3: Pharmacokinetic, ATA, and biomarker blood sample collection timepoints

	Study Day	Time	Window	Relative Time	PK	ATA	Blood				
							Biomarkers				
							Plasma		PBMC		
Cycles 1 and 2	Day 1	Pre-dose	within 24 hr	START of infusion	X	X	X	X	X	X	X
		End of infusion	within 15 min	END of infusion	X						
	Day 3	48 hr	±24 hr	END of Day 1 infusion	X		X ^a		X ^a	X ^a	X ^a
	Day 8	Pre-dose	within 24 hr	START of infusion	X		X ^a				
		End of infusion	within 15 min	END of infusion	X						
	Day 15	Pre-dose	within 24 hr	START of infusion	X		X ^a		X ^a	X ^a	X ^a
		End of infusion	within 15 min	END of infusion	X						
	Day 17	48 hr	-24 hr/+48 hr	END of Day 15 infusion	X						
	Day 22	168 hr	±48 hr	END of Day 15 infusion	X						
Subsequent dosing cycles	Day 1	Pre-dose	within 24 hr	START of infusion	X ^b	X ^b	X ^c				
End of Treatment (within 30–37 days of last dose)					X	X	X	X	X	X	X

a Cycle 1 only

b Cycles 3 and 4 and every even-numbered cycle thereafter

c Cycles 3 and 4 only

7.4.2 Biomarkers in Pre-Treatment Tumor Tissue

To better understand relationships between pre-treatment urothelial carcinoma biological characteristics, and patient outcome, submission of a tumor block or freshly sectioned, unstained charged slides (at least 10 slides are mandatory unless prior approval is obtained from the sponsor) of pretreatment tumor tissue are required. Either archival tissue or pre-treatment fresh tumor tissue (obtained from a fresh biopsy) is acceptable. See the Laboratory Manual for details.

Biomarker assessments in tumor tissue may include, but not be limited to:

- Tumor expression of Nectin-4 protein
- Messenger ribonucleic acid (mRNA) expression
- Markers of disease subtype (e.g., The Cancer Genome Atlas [TCGA] subtypes)
- Tumor mutational burden
- Markers of the tumor immune microenvironment

7.5 Biospecimen Repository

In the US only, for patients who provide additional consent, remaining de-identified unused blood and/or tissue will be retained by the sponsors and used for future research, including but not limited to the evaluation of targets for novel therapeutic agents, the biology of ADC sensitivity and resistance mechanisms, and the identification of biomarkers for ADCs. Blood and tissue samples donated for future research will be retained for a period of up to 25 years. If additional consent is not provided, any remaining biological samples will be destroyed following study completion and when the samples are no longer required to be maintained for potential regulatory submissions.

7.6 Quality of Life

Two validated tools will be used: the QLQ-C30, and the EQ-5D.

If possible, PRO assessments should be completed before any other procedures at the study visits noted in the schedule of events ([Appendix A](#)).

7.6.1 EORTC Core Quality of Life Questionnaire, QLQ-C30

The QLQ-C30 was developed to measure aspects of QoL pertinent to patients with a broad range of cancers who are participating in clinical trials ([Aaronson 1993](#); [Sneeuw 1998](#)). The current version of the core instrument (QLQ-C30, Version 3) is a 30-item questionnaire consisting of the following:

- 5 functional domains (physical, role, cognitive, emotional, social);
- 3 symptom scales (fatigue, pain, nausea & vomiting);

- Single items for symptoms (shortness of breath, loss of appetite, sleep disturbance, constipation, diarrhea) and financial impact of the disease; and
- 2 global items (health, overall QoL).

7.6.2 EuroQol-5 Dimensions

The EQ-5D is a standardized instrument developed by the EuroQol Group for use as a generic, preference-based measure of health outcomes. It is applicable to a wide range of health conditions and treatments and provides a simple descriptive profile and a single index value for health status. The EQ-5D is a 5-item self-reported measure of functioning and well-being, which assesses 5 dimensions of health, including mobility, self-care, usual activities, pain/discomfort, and anxiety/depression. Each dimension comprises 3 levels (no problems, some/moderate problems, extreme problems). A unique EQ-5D health state is defined by combining 1 level from each of the 5 dimensions. This questionnaire also records the respondent's self-rated health status on a vertical graduated (0 to 100) visual analogue scale. Responses to the 5 items will also be converted to a weighted health state index (utility score) based on values derived from general population samples. The EQ-5D is recommended for use in cost-effectiveness analyses commonly employed in health technology assessments by the Washington Panel on Cost Effectiveness in Health and Medicine ([Gold 1996](#)).

7.7 Safety Assessments

The assessment of safety during the course of this study will consist of the surveillance and recording of AEs including SAEs, recording of concomitant medication, and measurements of protocol-specified physical examination findings, cardiac monitoring, and laboratory tests.

Safety will be monitored over the course of the study by an IDMC as described in [Section 9.3.10](#).

7.7.1 Adverse Events

7.7.1.1 Definitions

Adverse Event

According to the International Council for Harmonisation (ICH) E2A guideline Definitions and Standards for Expedited Reporting, and 21 Code of Federal Regulations (CFR) 312.32, Investigational New Drug (IND) Safety Reporting, an AE is any untoward medical occurrence in a patient or clinical investigational subject administered a medicinal product and which does not necessarily have a causal relationship with this treatment.

The following information should be considered when determining whether or not to record a test result, medical condition, or other incident on the Adverse Events and Pre-existing Conditions CRF:

- From the time of informed consent through the day prior to study Day 1, only study protocol-related AEs should be recorded. A protocol-related AE is defined as an untoward medical event occurring as a result of a protocol mandated procedure.
- All medical conditions present or ongoing predose on study Day 1 should be recorded.
- All AEs (regardless of relationship to study drug) should be recorded from study Day 1 (pre-dose) through the end of the safety reporting period (see [Section 7.7.1.3](#)). Complications that occur in association with any procedure (e.g., biopsy) should be recorded as AEs whether or not the procedure was protocol mandated.
- Changes in medical conditions and AEs, including changes in severity, frequency, or character, during the safety reporting period should be recorded.
- In general, an abnormal laboratory value should not be recorded as an AE unless it is associated with clinical signs or symptoms, requires an intervention, results in a SAE, or results in study termination or interruption/discontinuation of study treatment. When recording an AE resulting from a laboratory abnormality, the resulting medical condition rather than the abnormality itself should be recorded (e.g., record “anemia” rather than “low hemoglobin”).

Serious Adverse Events

An AE should be classified as an SAE if it meets one of the following criteria:

Fatal:	AE resulted in death
Life threatening:	The AEs placed the patient at immediate risk of death. This classification does not apply to an AE that hypothetically might cause death if it were more severe.
Hospitalization:	The AE resulted in hospitalization or prolonged an existing inpatient hospitalization. Hospitalizations for elective medical or surgical procedures or treatments planned before the signing of informed consent in the study or routine check-ups are not SAEs by this criterion. Admission to a palliative unit or hospice care facility is not considered to be a hospitalization. Pre-planned hospitalizations for therapeutic, diagnostic, or surgical procedures of the underlying cancer or study target disease that did not worsen during the clinical trial need not be captured as SAEs.
Disabling/incapacitating:	An AE that resulted in a persistent or significant incapacity or substantial disruption of the patient’s ability to conduct normal life functions.
Congenital anomaly or birth defect:	An adverse outcome in a child or fetus of a patient exposed to the molecule or study treatment regimen before conception or during pregnancy.
Medically significant:	The AE did not meet any of the above criteria, but could have jeopardized the patient and might have required medical or surgical intervention to prevent one of the outcomes listed above or involves suspected transmission via a medicinal product of an infectious agent.

Adverse Event Severity

AE severity should be graded using the National Cancer Institute's Common Terminology Criteria for Adverse Events (NCI CTCAE), Version 4.03. These criteria are provided in the study manual.

AE severity and seriousness are assessed independently. 'Severity' characterizes the intensity of an AE. 'Serious' is a regulatory definition and serves as a guide to the sponsor for defining regulatory reporting obligations (see definition for SAEs, above).

Relationship of the Adverse Event to Study Treatment

The relationship of each AE to enfortumab vedotin should be evaluated by the investigator using the following criteria:

Related:

There is evidence to suggest a causal relationship between the drug and the AE, such as:

- A single occurrence of an event that is uncommon and known to be strongly associated with drug exposure (e.g., angioedema, hepatic injury, Stevens-Johnson Syndrome)
- One or more occurrences of an event that is not commonly associated with drug exposure, but is otherwise uncommon in the population exposed to the drug (e.g., tendon rupture)

Unrelated:

Another cause of the AE is more plausible (e.g., due to underlying disease or occurs commonly in the study population), or a temporal sequence cannot be established with the onset of the AE and administration of the study treatment, or a causal relationship is considered biologically implausible

7.7.1.2 Procedures for Eliciting and Recording Adverse Events

Investigator and study personnel will report all AEs and SAEs whether elicited during patient questioning, discovered during physical examination, laboratory testing and/or other means by recording them on the CRF and/or SAE form, as appropriate.

Eliciting Adverse Events

An open-ended or non-directed method of questioning should be used at each study visit to elicit the reporting of AEs.

Recording Adverse Events

The following information should be recorded on the Adverse Events and Pre-existing Conditions CRF:

- Description including onset and resolution dates
- Whether it met SAE criteria
- Severity
- Relationship to study treatment or other causality
- Outcome

Diagnosis vs Signs or Symptoms

In general, the use of a unifying diagnosis is preferred to the listing out of individual symptoms. Grouping of symptoms into a diagnosis should only be done if each component sign and/or symptom is a medically confirmed component of a diagnosis as evidenced by standard medical textbooks. If any aspect of a sign or symptom does not fit into a classic pattern of the diagnosis, report the individual symptom as a separate adverse event.

Important exceptions for this study are adverse reactions associated with the infusion of study drug. For IRRs, record the NCI CTCAE term of ‘infusion related reaction’ with an overall level of severity (per NCI CTCAE). In addition, record each sign or symptom of the reaction as an individual AE. If multiple signs or symptoms occur with a given infusion-related event, each sign or symptom should be recorded separately with its level of severity.

Recording Serious Adverse Events

For SAEs, record the event(s) on both the CRF and an SAE form.

The following should be considered when recording SAEs:

- Death is an outcome of an event. The event that resulted in the death should be recorded and reported on both an SAE form and CRF.
- For hospitalizations, surgical, or diagnostic procedures, the illness leading to the surgical or diagnostic procedure should be recorded as the SAE, not the procedure itself. The procedure should be captured in the narrative as part of the action taken in response to the illness.

Progression of the Underlying Cancer

Do not report radiographic signs of disease progression (e.g., ‘tumor progression’ or ‘metastases’) as an AE (this data is captured in the efficacy assessment). Report the symptoms and signs of disease progression (e.g., “fatigue”, “dyspnea”) as AEs; do not report disease progression as the AE term.

For disease progression with a fatal outcome, report the immediate cause of death as the event term. If the immediate cause of death cannot be determined and it is thought by the investigator to be related to disease progression, report the AE using the term ‘disease progression’ with a fatal outcome.

Pregnancy

Notification to Drug Safety: Complete a Pregnancy Report Form for all pregnancies that occur from the time of first study drug dose until 6 months after the last dose of study drug(s) including any pregnancies that occur in the partner of a male study patient. Only report pregnancies that occur in a male patient’s partner if the estimated date of conception is after the male patient’s first study drug dose. Email or fax to the sponsor’s Drug Safety Department within 48 hours of becoming aware of a pregnancy. All pregnancies will be

monitored for the full duration; all perinatal and neonatal outcomes should be reported. Infants should be followed for a minimum of 8 weeks.

Collection of data on the CRF: All pregnancies (as described above) that occur within 30 days of the last dose of study drug(s) will also be recorded on the Adverse Events and Pre-Existing Conditions CRF.

Abortion, whether accidental, therapeutic, or spontaneous, should be reported as an SAE. Congenital anomalies or birth defects, as defined by the ‘serious’ criterion above (see definitions [Section 7.7.1.1](#)) should be reported as SAEs.

Corneal Adverse Events

Corneal ulcer or keratitis AEs \geq Grade 2 should be graded within their respective categories. Grade 1 corneal ulcer or keratitis AEs should be graded per “Eye disorders – Other, specify” criteria. Other corneal AEs should be recorded and graded per “Eye disorders – Other, specify” criteria.

Adverse Events of Possible Hepatic Origin

If an AE is accompanied by increases in LFT values (e.g. AST, ALT, bilirubin, etc.) or is suspected to be due to hepatic dysfunction, see [Appendix E](#) for detailed information on recommended monitoring and assessment of liver abnormalities. See [Section 5.2.3.1](#) for treatment discontinuation recommendations related to hepatic safety.

Patients with AEs of hepatic origin accompanied by LFT abnormalities should be carefully monitored.

7.7.1.3 Reporting Periods for Adverse Events and Serious Adverse Events

The safety reporting period for all AEs and SAEs is from study Day 1 (predose) through 30 days after the last study treatment. However, all study protocol-related AEs are to be recorded from the time of informed consent. All SAEs that occur after the safety reporting period and are considered study treatment-related in the opinion of the investigator should also be reported to the sponsor.

SAEs will be followed until significant changes return to baseline, the event stabilizes (recovering/resolving) or is no longer considered clinically significant by the investigator, or the patient dies or withdraws consent. All non-serious AEs will be followed through the safety reporting period. Certain non-serious AEs of clinical interest may be followed (including collection of relevant concomitant medications) until resolution, return to baseline, study closure, or the events become chronic to the extent that they are adequately characterized.

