7.6.1.1 Adverse Events of Special Interest

Peripheral neuropathy, corneal events, hyperglycemia, dermatological reactions, and infusion related reactions (IRR) are considered adverse events of special interest (AESI) for enfortumab vedotin. These are medical concepts of composite terms based on the search criteria (standard MedDRA query [SMQ] or sponsor specified query [SSQ]). Other AEs may be added to AESI as necessary. The search criteria for AESI will be maintained in a separate document and finalized prior to final database lock.

Treatment-emergent AESI will be summarized by PT and maximum severity. In addition, serious AESI, treatment-emergent AESI that are related to study drug, leading to dose modification and study treatment discontinuation will be summarized.

For selected AESI, time to onset, improvement, or resolution will be analyzed as appropriate.

Time to onset of a specific AESI will be calculated as time from the first dose of study drug to the start of first treatment-emergent event that meets the respective search criteria. In the analysis of time to onset of AE of a specific grade (e.g., grade 3 or higher), episode of events that are improved from a previous higher grade will not be included.

Resolution is defined as event outcome of ‘recovered/resolved’ or ‘recovered/resolved with sequelae’, or returning to baseline grade as of the latest assessment for conditions that are ongoing at baseline. For events with an outcome of ‘recovered/resolved’ or ‘recovered/resolved with sequelae’, time to resolution will be calculated as time from the event start date to end date. For events that return to baseline grade, time to resolution will be calculated as time from the start of treatment-emergent event to the date the event was last assessed.

For events that are not resolved, improvement is defined as decrease by at least one grade from the worst grade as of the latest assessment. For events that meet the definition of ‘improvement’, time to improvement will be calculated as time from the worst grade of the event to the date the event was last assessed.

Time to onset will be summarized at the subject level. Time to resolution and improvement will be summarized at the event level.

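### AESI time to resolution is defined only for events that resolved, with no censoring rule for the rest, so a summary built on these definitions runs short for slow toxicities such as neuropathy

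*Protocol*

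**What the plan says.** **Length of follow-up (Protocol 7.7.1.3).** The reporting window is fixed: "The safety reporting period for all AEs and SAEs is from study Day 1 (predose) through 30 days after the last study treatment". For non-serious events the default is "All non-serious AEs will be followed through the safety reporting period". An extension is allowed: "Certain non-serious AEs of clinical interest may be followed (including collection of relevant concomitant medications) until resolution, return to baseline, study closure", or until the event is chronic and adequately characterised. The events that qualify are not named, and nothing links them to the SAP's AESI list. Serious events have their own, longer rule: "SAEs will be followed until significant changes return to baseline, the event stabilizes (recovering/resolving) or is no longer considered clinically significant by the investigator", or until death or withdrawal of consent.

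**Analysis (SAP 7.6.1.1).** The AESI are listed: "Peripheral neuropathy, corneal events, hyperglycemia, dermatological reactions, and infusion related reactions (IRR) are considered adverse events of special interest (AESI"). For selected AESI, time to onset, improvement or resolution is to be analysed as appropriate; no estimator is named. For events with a recovered outcome, "time to resolution will be calculated as time from the event start date to end date". For conditions present at baseline that return to baseline grade, the time runs to the date of last assessment. Unresolved events that fell by at least one grade get a time to improvement. Finally, "Time to resolution and improvement will be summarized at the event level".

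**Censoring and missing dates.** SAP 6.5 refers censoring of time-to-event endpoints to Section 7.5, which covers efficacy only. SAP Appendix A imputes no end date for a last record whose outcome is recovering, not recovered, unknown or blank.

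**The concern.** An event that has neither resolved nor improved has no time in either summary. Whether an event resolves while under observation depends on how long it is watched, so the times that remain are selected for being short. The effect is largest where the required window is shortest: an event that starts near the last dose, or that leads to stopping treatment. Protocol 1.6 lists peripheral neuropathy among the events that led to discontinuation in the phase 1 study (2 patients).

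At stake is what the study report says about the reversibility of AESI. Safety and tolerability is a secondary objective. A resolved-only median can make a slow toxicity look like a fast one, because it mainly reflects the observation window. The primary endpoint, the AE incidence tables and the trial's decisions are not affected.

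**Working it through.** The documents state no figure for AE resolution time, so there is none to reproduce. The check has two parts.

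**1. Which events get a time under the SAP's definitions?**

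| Status at last assessment | Time to resolution | Time to improvement |
|---|---|---|
| Recovered, with or without sequelae | start to end date | not applicable |
| Back to baseline grade (condition present at baseline) | start to last assessment | not applicable |
| Unresolved, at least one grade better than worst | none | worst grade to last assessment |
| Unresolved, not improved | none | none |

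No rule in SAP 6.5, 7.6.1.1 or Appendix A gives the last two rows a censored resolution time. One imputation rule also pulls dates towards the window: a resolved last record with only a year for its end date, in the year of the last dose, is dated no later than last dose + 30 days.

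**2. What does a resolved-only median show?**

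Input from the documents: the required window for a non-serious event starting on day s, with last dose on day L, is C = L − s + 30 days. Assumptions: exponential time to resolution with true median M; no use of the optional extension; no serious events.

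For a fixed window C:
- share resolved F = 1 − 2^(−C/M)
- median among resolved = −ln(1 − F/2) × M / ln 2

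Example, M = 180 and C = 90: F = 1 − 2^(−0.5) = 0.293. The median among resolved is −ln(0.8535) × 180/0.6931 = 41 days.

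| True median (days) | C = 30: resolved, median | C = 90: resolved, median | C = 180: resolved, median |
|---|---|---|---|
| 30 | 50%, 12.5 | 88%, 25 | 98%, 29 |
| 90 | 21%, 14.1 | 50%, 37 | 75%, 61 |
| 180 | 11%, 14.6 | 29%, 41 | 50%, 75 |
| 365 | 5%, 14.8 | 16%, 43 | 29%, 82 |

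For slow events the median among resolved approaches C/2, whatever the true median is.

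A mix of early and late onsets is more realistic. With onset uniform over D treatment days, C runs from 30 to D + 30. Simulation of 400,000 events per scenario, D = 140:

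| True median (days) | Resolved | Resolved-only median | Kaplan-Meier median |
|---|---|---|---|
| 60 | 65% | 34 | 60 |
| 90 | 51% | 39 | 90 |
| 180 | 31% | 45 | not reached |
| 365 | 17% | 48 | not reached |

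Check on the third row: λ = ln 2/180 = 0.003851, and the expected share resolved is 1 − (e^(−30λ) − e^(−170λ))/(140λ) = 1 − (0.891 − 0.520)/0.539 = 0.31, which agrees.

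For D = 84 to 196, a true median of 180 days gives a resolved-only median of 33 to 56 days, and 365 days gives 35 to 61. As the true median rises about sixfold, from 60 to 365 days, the resolved-only median at D = 140 moves only from 34 to 48. Kaplan-Meier on the same data recovers the true median or shows that it was not reached.

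**The case against.** Several points on the other side stand.

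- **The estimator is open.** A reader might infer that the SAP prescribes a median of resolved events only. It does not: analysis as appropriate neither requires nor excludes Kaplan-Meier. The supportable statement is that no censored method is specified and that the definitions reach only resolved or improved events.
- **Follow-up need not stop at 30 days.** A reader might infer that a neuropathy resolving at month 4 will be recorded as unresolved. That holds only where the extension is not used, since "Certain non-serious AEs of clinical interest may be followed" to resolution. The Amendment 5 rationale even describes such follow-up as a requirement, though a change log is not operative text. Serious AESI are followed beyond 30 days, and an early-onset event is observed for the rest of treatment plus 30 days.
- **Site choice is not in the text.** A reader might infer that the percentage resolved depends on which sites keep following. The protocol does not say who decides.
- **There is an offset.** Events back at baseline grade are timed to last assessment, which can lengthen some times.
- **The output is descriptive.** Time to resolution is not a listed endpoint, and it covers selected AESI only.

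These points limit how far the bias can be predicted. They do not supply a rule for unresolved events, and that is the gap.

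**Conclusion.** The point holds as a gap in the SAP. Followed literally, 7.6.1.1 leaves slow events out of the resolution summary, and the result is biased short. The direction follows from the definitions. The size cannot be derived from the documents: it depends on the true resolution times, when events start, how often follow-up is extended and how many events are serious. The 34, 39 and 45 days for true medians of 60, 90 and 180 days are illustrations under exponential resolution, uniform onset over 140 days and no extension. Assuming that every event is watched for only a few weeks would give a larger bias, but the documents do not support that as the general case.

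A reader might also infer that the protocol must make extended AESI follow-up mandatory. The documents do not establish this. After progression or new therapy, the contacts in Protocol 6.7 and 7.8.2 collect only survival status and subsequent therapy, so grading an AESI there would add burden. Status after new therapy would also reflect other drugs. The analysis can be corrected with the data already planned.

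**What to change.** In SAP 7.6.1.1, for the selected AESI:

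1. Estimate time to resolution by Kaplan-Meier over all treatment-emergent episodes, resolved or not.
2. Censor unresolved episodes at the earlier of the last AE status date and the start of subsequent anticancer therapy.
3. Treat death as a competing event, reporting the cumulative incidence of resolution, or censor at death and say so.
4. Allow for several episodes per subject, for example with subject-clustered confidence intervals, or by using the first or worst episode per subject.
5. Report beside the estimate the number and percentage unresolved at last assessment and the length of follow-up.
6. Label any resolved-only median as conditional on resolution.

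The cost is a small amount of extra analysis and no new data. Medians will be less favourable, and some will not be reached. Kaplan-Meier still assumes that the end of observation is unrelated to the course of the event, which is why follow-up length should be shown. Requiring longer follow-up of ongoing AESI in Protocol 7.7.1.3 would add information, but it is optional and the SAP change does not depend on it.
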